### **5.0 Study Design**

This is a 16-week pilot, prospective, cross over study to meet the objective of the study where the novel EMTS based digital weight bearing system will be compared to SoC non-weight bearing socket design for improving limb health and functional outcomes post 6 weeks use. The subject (n=12) lower extremity unilateral trans-tibial subjects will participate in both study arms sequentially: Arm 1 (SoC- non-weight bearing): and Arm 2: EMTS based shape capture in full weight bearing using (SADS, Symphonie Aqua Digital System, Romedis GmbH).

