#### **5.1 Enrollment**

The subject (n=12) lower extremity unilateral trans-tibial subjects will begin the study on Arm 1 (SoC- non-weight bearing (Socket A) : and then move to Arm 2: EMTS based shape capture in full weight bearing using (SADS, Symphonie Aqua Digital System, Romedis GmbH, Socket B).

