#### **5.2 Study Procedures**

**Study Visit 1a-c (Initial Evaluation/Fitting; Weeks 0-6):** Immediately post-enrollment, socket shape capture will be completed with Digital and non-digital weight bearing Aqua systems. Baseline measurement for SoC will be performed. The following baseline measurements will be performed for SoC Socket (Socket A) at this first visit:

- TEWL measurement
- Laser Speckle Flowmetry (LSI)
- In-Socket Sensors
- Motion Capture Analyses
- 6 Minute Walk Test (6MWT)
- Timed Up-and-Go (TUG)
- Houghton Scale

- **Socket Comfort Score**
- **Veterans RAND 36-Item Health Survey**

The fitting of the digital and non-digital weight bearing sockets will continue for up to 4-6 weeks to ensure proper fitting of the weight bearing socket and comfortability during this time the subjects will continue to use their SoC socket A.

**Study Visit 2 – SoC final visit (week 6 +/- 2 Weeks):** Participants will return to the hospital. Participants will be asked to wear clothing that is comfortable for them while they may be participating in physical activity prior to attending the visit. Study members will offer specific guidance on study if necessary. If they do not have any comfortable clothing, they will be asked to speak with research personnel. Research personnel will provide them with the appropriate clothing if they are unable to bring any during this visit. The following procedures will be performed during this visit with their Socket B.

- **TEWL measurement**
- **Laser Speckle Flowmetry (LSI)**
- **In-Socket Sensors**
- **Motion Capture Analyses**
- **6 Minute Walk Test (6MWT)**
- **Timed Up-and-Go (TUG)**
- **Houghton Scale**
- **Socket Comfort Score**
- **Veterans RAND 36-Item Health Survey**

At this visit, the definitive **socket B** will be ready & fitted; the measurements in this visit will serve **as the baseline visit values for Socket B**; End of this visit the participants will start using the Socket B for next 6 weeks Study members will offer specific guidance on study as necessary.

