## **10.0 Statistical Considerations**

This is a pilot study that is expected to generate preliminary data that will inform sample size for an adequately powered phase 2 study (in future). In this study, a total of n=12 subjects will be enrolled.

In general, for continuous data, means, median, standard deviations, and range will be provided. For categorical data, the count and frequency will be provided. In general, inferential tests will be tested with two-sided p-values or 95% confidence intervals, unless otherwise stated. Missing data distributions and patterns will be checked, and in the scenario of missing at random (MAR), we will consider multiple imputation procedures in data analysis. For Aim 1, TEWL values will be used as a function of overall limb health and as our primary endpoint. In addition to the primary endpoint, the secondary endpoint Laser Speckle Imaging will also be examined in aim 1. All of these endpoints are measured or quantified into continuous scale that would be used as outcomes. For Aim 2, functional outcomes will be evaluated using 2MWT and TUG, at baseline and at 6 weeks period post-socket use. To test the hypothesis, all these functional measurements will be transformed into standardized Z-scores with mean of 0 and a standard deviation of 1. These standardized scores will then be pooled into one composite score to quantify standardized functional score. The patient reported outcomes (PRO) will be assessed using validated instruments: Summary measures will be derived by summation of item specific scores for each instrument. These summary measures from functional measures and PRO will then be transformed into standardized Z-scores to create a pooled (composite) score for the overall PRO. For functional and PRO measure, generalized linear mixed methods with carryover effect, if any, will be used to examine the effect of types of socket on composite measure of the measures. A profile plot of the mean (or median) of each continuous endpoint variable will be created over follow-up time for each arm of the test-socket. All analyses will be done using SAS 9.4 or Stata 16.0 or higher.

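### All 12 subjects go from Socket A to Socket B, so the Aim 2 carryover term rests on unstated assumptions, the socket effect includes time and new-socket effects, and the Visit 2 text leaves socket-dependent measures without an end-of-period Socket A value

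*Combined protocol and SAP*

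**What the plan says.** Section 5.0 describes the design: "This is a 16-week pilot, prospective, cross over study". It sets the two socket types against each other after six weeks of use. Section 5.1 fixes the order: all 12 subjects "will begin the study on Arm 1 (SoC- non-weight bearing (Socket A) : and then move to Arm 2". Sections 5.0 to 5.2 describe no reverse sequence and no washout.

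Socket A is the socket the subject already has. While Socket B is being fitted, "during this time the subjects will continue to use their SoC socket A". The procedure details in Section 5.2 nevertheless say that shape capture is all that distinguishes the two sockets.

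Section 5.2 heads Visit 2 as "SoC final visit (week 6 +/- 2 Weeks". The text beneath says "The following procedures will be performed during this visit with their Socket B", assigns the values a role "as the baseline visit values for Socket B", and adds: "End of this visit the participants will start using the Socket B for next 6 weeks". Visit 3, at week 12 +/- 2, is measured with Socket B.

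For Aim 2, Section 10.0 plans this: "For functional and PRO measure, generalized linear mixed methods with carryover effect, if any, will be used to examine the effect" of socket type on the composite scores. It does not define carryover, names no period or time term, and states no identifying assumption. It names no model for TEWL, the primary endpoint, or for laser speckle imaging (LSI).

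**The concern.** A carryover term belongs to a design in which treatment order varies between subjects. Here order, calendar time and socket move together. A model that includes carryover may not be estimable. A model that drops it under the plan's own conditional wording gives a before-after change and labels it a socket effect.

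Two features make this more than formal. First, the plan supplies a reason to expect drift: Section 4.1 admits subjects from 3 months after amputation, and Section 1.0 says the residual limb changes during the first 12 to 18 months. The share of recent amputees is unknown. Second, only Socket B is newly made and fitted, so any benefit of a fresh socket counts towards the weight-bearing method.

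Efficacy against standard of care is the primary objective (Section 2.1), Section 10.0 plans inferential tests, and the results are meant to inform the size of a phase 2 study. The Visit 2 conflict adds to this: if Visit 2 belongs to Socket B, the comparison in Section 5.0 has no six-week Socket A value for measures that depend on the socket being worn.

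**Working it through.** **Inputs.** n=12, one sequence, two-sided 95% intervals (Sections 5.1 and 10.0); nominal visits at weeks 0, 6 and 12 (Sections 5.2 and 6.0). The documents give no SD, trend or effect size, and no power figure to reproduce. Below, SD means the SD of the within-subject six-week change, and 12 completers are assumed.

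**Step 1: can carryover be estimated?** Let m be the Socket A mean at Visit 1, s the socket effect, c carryover, and d the drift per six weeks.

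If c lasts through Socket B use, every Socket B mean contains s + c and no Socket A mean contains either. Only the sum is estimable: rank 2 of 3 without a time term, whatever Visit 2 measures.

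If c is present only at the first Socket B visit, the rank of the fixed-effects matrix (intercept, socket, carryover, plus any time terms) is:

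| Visit 2 measures | No time term | Linear time | Visit factor |
|---|---|---|---|
| B only | 3 of 3 | 3 of 4 | 3 of 5 |
| A only | 2 of 3 | 3 of 4 | 3 of 5 |
| A and B | 3 of 3 | 4 of 4 | 4 of 5 |

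For example, with B only and linear time, the three means are m, m + d + s + c and m + 2d + s: four unknowns from three means. With both sockets at Visit 2, the means are m, m + d, m + d + s + c and m + 2d + s, which can be solved.

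These ranks hold at nominal weeks. With actual dates spread over the +/- 2 week windows, the B-only, linear-time model with subject effects reaches full rank (15 of 15). In simulated dates, however, the standard error for socket was about 7 to 8 times that of a socket-only model.

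**Step 2: what is the socket effect without carryover?** Let w be the effect of having a newly made socket. Then

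Socket B at week 12 - Socket A at week 6 = s + w + d.

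Subtracting the Visit 1 to Visit 2 change on Socket A removes d if drift is linear. Nothing in the design removes w, because every Socket B measurement is on a new socket and no Socket A measurement is: socket plus new-socket has rank 2 of 3 under every reading of Visit 2.

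**Step 3: which socket does each Visit 2 value belong to?** In-socket pressure, motion capture, the timed tests and the comfort score reflect the socket worn at that moment, which as written is B. TEWL is a skin probe and LSI images blood flow, on a limb that has worn A until that visit, so their values may largely reflect A. The text still lists them among the Socket B procedures and gives no order relative to the walking tests. No recall period is given for the Houghton Scale or the health survey.

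**Step 4: size, under assumed values.**
- Bias: with s = 0 and drift of 0.3 or 0.5 SD, a paired t test of Visit 3 against Visit 2 (noncentral t, 11 df, noncentrality drift x sqrt(12)) rejects 15.8% or 35.3% of the time.
- Drift check: the 95% half-width for the Visit 1 to Visit 2 change is 2.201 / sqrt(12) = 0.64 SD. Power reaches 80% only for drift of 0.89 SD.
- Change on B minus change on A, sharing one Visit 2 value: under AR(1) errors and equal drift, Var(Y3 - 2Y2 + Y1) / Var(Y3 - Y2) = (6 - 8rho + 2rho^2) / (2 - 2rho) = 3 - rho. The ratio is 3 at rho = 0 and approaches 2 as rho approaches 1. Power for an assumed 0.8 SD effect falls from 71% to between 31% and 43%.
- Those limits are not bounds. If drift differs between subjects, with slope variance k times the (independent) visit-error variance, the ratio is 6 / (2 + k): 2 at k=1 and 1 at k=4. With separate A and B values at Visit 2 and independent errors, it is 4/2 = 2.

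**The case against.** The strongest reply is that this is a declared pilot, that single-sequence studies are legitimate, and that the carryover term is conditional and confined to Aim 2. All of that is true. It limits the severity, but the conditional wording gives no way of telling carryover from socket or time.

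Three stronger readings are tempting, and the documents do not support them.

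- **Carryover can never be estimated.** It can, under the assumptions in Step 1. The literal text (B at Visit 2, no time term, carryover at that visit only) has full rank. Stating those assumptions would be an alternative to deleting the term, but assuming no time effect sits badly with the limb change described in Section 1.0.
- **The plan offers no contrast.** Section 5.0 does suggest one: the two sockets after six weeks of use. The fault is that Sections 5.2 and 10.0 do not carry it through.
- **TEWL has no control for time.** Section 5.2 schedules a contralateral reference measurement at matched sites. It could remove ambient or systemic drift, although Section 10.0 gives it no role. It cannot remove change in the residual limb or the effect of a new socket.

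It is also fair to say that the numerical illustrations use a paired t test where the plan has a mixed model, and that no drift or practice effect is documented.

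**Conclusion.** The point holds and should be fixed. The single sequence, the undefined carryover term and the conflicting Visit 2 text are all on the page. The rank results need no assumed effect size, but they are for nominal visit weeks. The false-positive and power figures depend on assumed drift, effect size and error structure, and show only what could happen.

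A reader might infer that the trial will overstate the benefit of Socket B, or that its results are unusable. Neither follows. The direction of any bias is unknown, and a before-after estimate labelled as such is a reasonable pilot result. What the design does not support is attributing the change to shape capture alone.

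**What to change.** 1. In Section 10.0, delete the carryover term. In Section 5.0, describe the study as a single-sequence before-after comparison.
2. Reconcile the Visit 2 text in Section 5.2 endpoint by endpoint, stating which socket each value refers to, so that the comparison in Section 5.0 has a Socket A value. Include TEWL, LSI and the questionnaires.
3. Name one contrast per endpoint: last Socket A value against the six-week Socket B value, with 95% CI. Beside it, report the Visit 1 to Visit 2 change on Socket A with its CI and actual weeks. The windows allow Visit 2 at weeks 4 to 8 and Visit 3 at weeks 10 to 14, hence 2 to 10 weeks between them if both count from enrolment. Treat this as a descriptive drift check, and do not read a non-significant change as no drift. State how the contralateral reference enters the TEWL analysis. Change on B minus change on A may be a sensitivity analysis, with its precision reported.
4. State that the contrast includes time, practice and new-socket effects, and qualify the Section 5.2 statement that only shape capture differs. Do not size phase 2 on the observed effect. If phase 2 is within-subject, use the within-subject SD with its CI: sqrt(11/chi-square) limits of 0.71 to 1.70 times the observed SD at n=12.

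Randomising the order would be an optional redesign. It would separate socket from period, but not from the new-socket effect while only Socket B is newly made.

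**Cost.** Items 1, 3 and 4 are wording and use measurements already scheduled. Item 2 is wording too if the team already knows which socket it intends at Visit 2. The price is a more modest claim and an imprecise drift check.

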## **11.0 Data Management**

**Clinical Data:** Will be recorded in RedCap (research electronic data capture (HIPAA compliant)) as clinical research database. Prior to being given access to the data, HIPAA and human subjects certified “study staff” will be trained in the collection of patient-reported outcomes. Study data will be collected using standardized case report forms (CRFs), with clear, uniform instructions for study staff. Researcher’s access to files will be governed by institutional secure data access policies. The redcap platform is developed and operated by IU clinical research IT team.

**Data Quality and Security:** The study team will review all CRFs. All incoming data will be monitored, with particular attention to: 1) enrollment and follow-up reports as entered into the database; 2) potential adverse events, and 3) missing data or extreme values. The clinical database administrator will generate reports of enrollment progress and data quality control results, to be distributed to the study team bi-monthly and ad hoc as needed, as well as to the safety committee.

## **12.0 Privacy/Confidentiality Issues**

Records of the participation in this study will be held confidential so far as permitted by law. Any information about participants will be obtained from this study will be kept confidential. The sponsor's delegates, IRB, and the United States Food and Drug Administration (FDA) have access to and may copy the medical records applicable for this study therefore absolute confidentiality cannot be guaranteed.

A description of this clinical trial will be available on <http://www.clinicaltrials.gov>, as required by U.S. law. This web site will not include information that can identify the participants. At most, the web site will include a summary of the results. The research study coordinator will have access to subject identity. All samples that will undergo analysis will only be identified by a subject code which can only be linked with protected health information (PHI) database by persons who have access to the study database (i.e., research nurses, investigators) via a password. This procedure satisfies HIPAA and is standard for clinical studies run at IU, and as overseen by the IU-CTSA.

## **13.0 Follow-Up/Record Retention**

Study results, data, and documentation will be stored for a minimum of 6 years.

## **14.0 Study Device FDA Status**

The proposed SADS under investigation is a device that will be used for socket fabrication for lower limb amputee. The device may eventually be included as part of the socket component and as such may fall under FDA class 1 . They fall under the FDA device description of "Component, External, Limb, Ankle/Foot" with FDA product code of "ISH". These products must be registered with the FDA prior to marketing, but they do not require 510(k) premarket clearance or Premarket approval (PMA). These devices incorporate significant improvements but they have substantial equivalence to existing products.

SADS combines individual socket production per the residual limb's anatomy while bearing the actual weight. By means of Magnetic Field Trackings, the actual form of the residual limb is hydrostatically captured in 3D while bearing full weight. The patients will place their residual limbs in the Symphonie aqua cylinder and can feel the water pressure. Once the patient is comfortable with the hydrostatic pressure, the magnetic tracking sensors will be activated by the prosthetist, the sensor data will be sent to the Central Control Unit. Based on the tracking data, the algorithm builds a 3D model of the prosthetic socket. The data may be directly sent to a 3D printer or to a Central Fabrication facility. The algorithm pre-calculates at which location and to what extent a patient's residual limb will change in the foreseeable future. Weight fluctuations, increased training frequency, water retention in body tissues as well as illness play a major role. Based on these values, a socket alteration is constructed and produced which is able to equalize the pre-calculated deviations. If required, this feature allows for the prosthetic socket to be again optimally fitted, based on the digital impression of the residual limb.
